6.4. Handling of Dropouts or Missing Data

Depending on the estimands being addressed, different methods will be used to handle missing data. Description of the estimands can be found in Section 6.2.

6.4.1. Handling of Dropouts or Missing Data for Induction Period

For efficacy analysis relative to the primary estimand, the primary method of handling missing data including those as a result of intercurrent events will be based on Markov Chain Monte Carlo Multiple Imputation (MCMC-MI). The description of MCMC-MI method can be found in Section 6.4.1.1. Tipping point analysis as described in Section 6.4.1.2 will serve as the sensitivity analysis for the primary analysis.

For efficacy analysis relative to the supportive estimand for categorical endpoints, missing data including those as a result of intercurrent events will be imputed as non-responder. The description of non-responder imputation (NRI) can be found in Section 6.4.1.3.

For efficacy analysis relative to the supportive estimand for continuous endpoints collected only once post-baseline, missing data including those as a result of intercurrent events will be imputed using Last Observation Carried Forward (LOCF). The description of LOCF can be found in Section 6.4.1.4.

For efficacy analysis relative to the supportive estimand for continuous endpoints collected multiple times post-baseline, a Mixed Model for Repeated Measures (MMRM) will be performed without explicit imputation. The description of MMRM can be found in Section 6.4.1.5.

Table KGAB.6.6 describes the planned imputation methods for efficacy and health outcome endpoints for Induction Period.

Table KGAB.6.6. Imputation Techniques for Various Variables During Induction Period

Type of Endpoints	Efficacy and Health Outcome Endpoints	Estimand (Analysis strategy for Intercurrent Events)	Missing Data Imputation Method (Analysis Method)
Categorical	IGA, EASI, Pruritus NRS, sleep loss and DLQI related categorical endpoints at pre-specified timepoints	Primary Estimand (Hybrid)	MCMC-MI, Tipping point analysis (CMH)
		Supportive Estimand (Composite)	NRI (CMH)
	Remaining categorical endpoints	Supportive Estimand (Composite)	NRI (CMH)
Continuous	EASI percent change, Pruritus NRS percent change, Sleep loss change from baseline, DLQI change from baseline	Primary Estimand (Hybrid)	MCMC-MI (ANCOVA)
		Supportive Estimand (Hypothetical)	No imputation (MMRM)
	Remaining continuous endpoints collected at multiple post-baseline timepoints including BSA, POEM and CDLQI	Supportive Estimand (Hypothetical)	No imputation (MMRM)
	Remaining continuous endpoints collected only once post-baseline	Supportive Estimand (Hypothetical)	LOCF (ANCOVA)

Abbreviations: ANCOVA = analysis of covariance; CMH = Cochran-Mantel-Haenszel; EASI = Eczema Area and Severity Index; IGA = Investigator's Global Assessment for AD; LOCF = last observation carried forward; MCMC-MI = Markov chain Monte Carlo multiple imputation; MMRM = mixed-model repeated measures; NRI = Nonresponder Imputation; NRS = Numeric Rating Scale.

6.4.1.1. Markov Chain Monte Carlo Multiple Imputation (MCMC-MI)

The primary method of handling missing efficacy data relative to the primary estimand will be as follows for both binary and continuous endpoints:

For patients who receive topical rescue medication (per Protocol Section 6.3), receive systemic rescue medication, or discontinue treatment due to lack of efficacy, set to the patient's baseline value subsequent to this time through Week 16. The MCMC-MI will be used to handle the remaining missing data. Imputation will be conducted within each treatment group independently so the pattern of missing observations in one treatment group cannot influence missing value imputation in another. The SAS PROC MI with MCMC option will be used to conduct the MCMC-MI. The imputation model will include the relevant baseline and post-baseline.

For each imputation process, 25 datasets with imputations will be calculated. The initial seed values are given in [Table KGAB.6.7](#). Each complete data set will be analyzed with the specified analysis. The results from these analyses will be combined into a single inference using SAS PROC MIANALYZE.

Cochran-Mantel-Haenszel (CMH) test statistic will be transformed using the Wilson-Hilferty transformation and then standardized (Ratitch 2013) prior to combining them using SAS PROC MIANALYZE. Details of combining estimates and test statistics for categorical endpoints with multiple imputation can be found in [Appendix 2](#).

For binary responses related to EASI and IGA, the binary response variables will be calculated based on the multiply imputed datasets that have been created. Because the MCMC algorithm is based on the multivariate normal model, imputed values for IGA will not generally be one of the discrete values used in IGA scoring (0, 1, 2, 3, or 4). Therefore, to derive the binary IGA response variable, standard rounding rules will be applied to the imputed values. For example, if a patient has an IGA score imputed as 1.4 (and assuming a Baseline IGA score of 3), the imputed value would be rounded down to 1, and the minimum change from Baseline of 2 would have been met. This patient would be considered a responder.

For derivation of an EASI-75 and EASI-90 response, no rounding will be performed. The imputed Week 16 EASI value will be compared directly to the observed Baseline EASI value to determine whether a reduction of at least 75% or 90% was achieved.

For derivation of the following Pruritus NRS responses, no rounding will be performed. The imputed Pruritus NRS value will be compared directly to the observed mean baseline Pruritus-NRS value to determine whether a response was achieved:

- Percentage of patients with a Pruritus NRS of ≥ 4 -points at Baseline who achieve a ≥ 4 -point reduction from Baseline at Weeks 1, 2, 4, and 16.

Imputation of continuous data will parallel that of binary variables. The imputed values will be used for the following secondary endpoints:

- Percentage change in Pruritus NRS score from Baseline to Week 16.
- Percentage change in EASI score from Baseline to Week 16.

Table KGAB.6.7. Seed Values for MCMC-MI for Induction Period

Analysis	Seed values Lebrikizumab 250 mg Q2W Placebo
Proportion of patients achieving IGA of 0 or 1 with a ≥ 2 -point improvement from baseline at Week 16	671970387 1339715635
Change and percent change from baseline in EASI score at 16 weeks. EASI-75 and EASI-90 will leverage imputation from EASI and therefore use the same seed numbers.	1015171075 1806114500
Change and percentage change in Pruritus NRS score from Baseline to Week 16. Proportion of patients achieving at least a 4-point improvement from baseline at Weeks 1, 2, 4, and 16 will leverage imputation from Pruritus NRS and therefore use the same seed numbers.	1461173528 1492214362
Change and percent change in Sleep loss from Baseline to Week 16. Proportion of patients achieving at least a 2-point improvement from baseline at Weeks 16 will leverage imputation from Sleep loss and therefore use the same seed numbers.	321568 765982
Change DLQI from Baseline to Week 16. Proportion of patients achieving at least a 4-point improvement from baseline at Weeks 16 will leverage imputation from DLQI and therefore use the same seed numbers.	458734 525683

Abbreviations: EASI = Eczema Area and Severity Index score; IGA = Investigator's Global Assessment for AD; MCMC = Markov chain Monte Carlo multiple imputation; NRS = Numeric Rating Scale; Q2W = every 2 weeks.

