## 9.4. Missing Data

The primary method of handling missing efficacy data will be as follows for both binary and continuous endpoints: for patients who receive topical rescue medication (per Section 6.3), receive systemic rescue medication or withdraw from the study due to lack of efficacy, set to the patient's baseline value subsequent to this time through Week 16. MCMC multiple imputation will be used to handle the remaining missing data. Imputation will be conducted within each treatment group independently so the pattern of missing observations in one treatment group cannot influence missing value imputation in another treatment group. For each imputation process, 25 datasets with imputations will be calculated. Each complete data set will be analyzed with the specified analysis. The results from these analyses will be combined into a single inference using SAS PROC MIANALYZE.

For binary responses related to EASI and IGA, the binary response variables will be calculated based on the multiply imputed datasets that have been created. Because the MCMC algorithm is based on the multivariate normal model, imputed values for IGA will not generally be one of the discrete values used in IGA scoring (0, 1, 2, 3, or 4). Therefore, to derive the binary IGA response variable, standard rounding rules will be applied to the imputed values. For example, if a patient has an IGA score imputed as 1.4 (and assuming a Baseline IGA score of 3), the imputed value would be rounded down to 1, and the minimum change from Baseline of 2 would have been met. This patient would be considered a responder.

For derivation of an EASI-75 response, no rounding will be performed. The imputed Week 16 EASI value will be compared directly to the observed Baseline EASI value to determine whether a reduction of at least 75% was achieved.

For derivation of the following Pruritus-NRS responses, no rounding will be performed. The imputed Pruritus-NRS value will be compared directly to the observed mean baseline Pruritus-NRS value to determine whether the response was achieved:

- Percentage of patients with a Pruritus NRS of  $\geq 4$ -points at Baseline who achieve a  $\geq 4$ -point reduction from Baseline to Week 16
- Percentage of patients with a Pruritus NRS of  $\geq 4$  points at Baseline who achieve a  $\geq 4$ -point reduction from Baseline to Week 4

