6.4.2.1. Maintenance Period MCMC-MI

The MCMC-MI will be used to handle missing data relative to the maintenance primary estimand (Hybrid) and maintenance supportive estimand (Hybrid) for both binary and continuous endpoints. Imputation will be conducted within each treatment group independently so the pattern of missing observations in one treatment group cannot influence missing value imputation in another. The SAS PROC MI with MCMC option will be used to conduct the MCMC-MI. The imputation model will include the relevant baseline and post-baseline.

For each imputation process, 25 datasets with imputations will be calculated. The initial seed values are given in [Table KGAB.6.7](#). Each complete data set will be analyzed with the specified analysis. The results from these analyses will be combined into a single inference using SAS PROC MIANALYZE.

Cochran-Mantel-Haenszel (CMH) test statistic will be transformed using the Wilson-Hilferty transformation and then standardized (Ratitch 2013) prior to combining them using SAS PROC

MIANALYZE. Details of combining estimates and test statistics for categorical endpoints with multiple imputation can be found in [Appendix 2](#).

The imputation and analysis will be conducted on Maintenance Primary Population only.

The derivation of binary responses related to EASI, IGA and Pruritus NRS for Maintenance Period will follow the derivation for Induction Period.

Table KGAB.6.10. Seed Values for MCMC-MI for Maintenance Period

Analysis	Seed values Lebrikizumab 250 mg Q2W/Q4W/ Placebo
IGA	12345
EASI	12346
Pruritus NRS score	12347

Abbreviations: EASI = Eczema Area and Severity Index score; IGA = Investigator's Global Assessment for AD; MCMC = Markov chain Monte Carlo multiple imputation; NRS = Numeric Rating Scale; Q2W = every 2 weeks; Q4W=every 4 weeks.

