6.11. Efficacy Analyses

[Table KGAB.6.11](#) includes the description and derivation of the efficacy/health outcomes measures and endpoints.

[Table KGAB.6.12](#) provides the detailed analyses relative to estimands including analysis type, method and imputation, population, time point, and treatment comparisons for efficacy/health outcomes analyses.

Table KGAB.6.11. Description and Derivation of Efficacy/Health Outcomes Measures and Endpoints

Measure	Description	Variable	Derivation / Comment	Imputation Approach if Missing Components
Investigator's Global Assessment (IGA)	The IGA is a static assessment and rates the severity of the patient's AD. The IGA is comprised of a 5-point scale ranging from 0 (clear) to 4 (severe) and a score is selected using descriptors that best describe the overall appearance of the lesions at a given time point.	IGA score	Single item. Range: 0 to 4 0 represents "clear" 4 represents "severe"	Single item, missing if missing.
		IGA [0,1] with ≥ 2 -point improvement	Observed score of 0 or 1 and change from baseline ≤ -2	Missing if baseline or observed value is missing. Single item, missing if missing.
		IGA [0]	Observed score of 0	
		Time to loss of IGA response, i.e., developing an IGA score ≥ 2 with 2 points deterioration of achieved IGA response at Week 16	Date of first time developing an increase in IGA score ≥ 2 compared to Week 16 - date of W16 re-randomization +1	If a patient has not experienced loss of IGA response by completion or early discontinuation of Maintenance Blinded Period or transfer to escape arm, the patient will be censored at the date of their last visit during Maintenance Blinded Period. If a patient has not experience loss of response by the time of systemic rescue during Maintenance Blinded Period, the patient will be censored at the date of systemic rescue.

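### Imputed IGA scores are rounded but not bounded, so a draw below the scale can be counted as non-response; the effect is small at Week 16 and somewhat larger at Week 52

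*SAP*

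**What the plan says.** SAP 6.4.1.1 acknowledges that normal draws will not fall on the five IGA grades ("Because the MCMC algorithm is based on the multivariate normal model") and names rounding as the only remedy: "to derive the binary IGA response variable, standard rounding rules will be applied to the imputed values". Its one worked example is a draw of 1.4 with a baseline of 3, which rounds to 1 and counts as response. The software statement is "The SAS PROC MI with MCMC option will be used to conduct the MCMC-MI", with no minimum or maximum given. Protocol 9.4 has the same text: "standard rounding rules will be applied to the imputed values".

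Table KGAB.6.11 in SAP 6.11 derives IGA response as "Observed score of 0 or 1 and change from baseline ≤ -2", and IGA [0] as a score of exactly 0.

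For the Maintenance Period, SAP 6.4.2.1 adds: "The derivation of binary responses related to EASI, IGA and Pruritus NRS for Maintenance Period will follow the derivation for Induction Period".

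Patients with rescue use or discontinuation for lack of efficacy in induction are set to baseline. The rounding rule therefore touches only the remaining missing values.

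**The concern.** Rounding makes a value whole; it does not put it on the scale. A draw of -0.7 becomes -1. With baseline IGA 3 or 4 this easily meets the two-point reduction, but -1 is neither 0 nor 1. The plan's example of 1.4 is a responder, while a lower and therefore better draw is, on a literal reading, a non-responder.

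Only IGA has this problem. EASI-75, EASI-90 and the pruritus response are one-sided thresholds on change, so a below-scale draw still counts as success. A draw above 4.5 does no harm to IGA either, because it is non-response under any coding.

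The endpoints touched are the primary IGA 0/1 endpoint, IGA [0], and the Week 52 IGA endpoint in the EMA maintenance hierarchy (SAP 6.6.2). The seeds and the 25 imputations are fixed in advance, yet the reported rate could still depend on how one line is coded.

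**Working it through.** **Planning anchor.** The documents give no figure for out-of-range draws. The nearest usable figures are the planning rates in SAP 5.2: 34.7% against 7.7%, with 96 and 48 patients said to give more than 95% power (continuity-corrected chi-square, two-sided 0.05). For 95% power:

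- Pooled rate = (0.077 + 2 × 0.347)/3 = 0.257; difference d = 0.27.
- Uncorrected placebo n = [1.96 × √(0.257 × 0.743 × 1.5) + 1.645 × √(0.077 × 0.923 + 0.347 × 0.653/2)]² / 0.27² = 42.3.
- Corrected n = (42.3/4) × [1 + √(1 + 3/(42.3 × 0.27))]² = 47.7, so 48.

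The plan's figure is reproduced (95.2% power at 96/48), and the rates can be used below.

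**Share of imputed Week 16 values below -0.5.** Take a normal draw whose chance of falling below 1.5 (rounding to 1 or less) equals the response rate r. Its mean is 1.5 - z(r) × SD, where z(r) is the normal quantile of r, so

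P(draw < -0.5) = Φ(z(r) - 2/SD).

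The SD of IGA is not in the documents; 0.8 to 1.3 is assumed.

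| SD | Lebrikizumab, r = 0.347 | Placebo, r = 0.077 |
|---|---|---|
| 0.8 | 0.19% | 0.004% |
| 1.0 | 0.84% | 0.03% |
| 1.1 | 1.35% | 0.06% |
| 1.3 | 2.67% | 0.15% |

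The lebrikizumab share is about 18 to 48 times the placebo share.

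**Effect on the Week 16 rate.** Loss = (share of patients imputed) × (share of draws below -0.5), with the imputed share assumed to be 5-20%.

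- Low: 5% × 0.84% = 0.04 points (SD 1.0).
- High: 20% × 2.67% = 0.53 points (SD 1.3), or 1.4 of 267 patients.
- Placebo over the same range: 0.002 to 0.03 points.

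The same draws are lost from IGA [0], so its absolute loss is the same.

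**Simulation check.** IGA trajectories were simulated near the planning rates, with a normal model fitted by arm and 25 imputations. At 10% missing the lebrikizumab rate was 34.38% with the literal coding and 34.47% with bounding. The gap of 0.09 points is about a quarter of one patient in 267. Placebo did not change. A second simulation under different assumptions put about 2% of imputed lebrikizumab values below -0.5, for a loss of 0.1 to 0.3 points at 5-20% missing.

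**Power.** At about 400 patients, power stays above 99.99% throughout. This includes an extreme case with 20% of lebrikizumab patients imputed and 20% of those draws lost (20% × 20% = 4.0 points).

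**Week 52.** The analysed patients all had IGA 0 or 1 at Week 16. Topical rescue is set to missing under the maintenance primary estimand, so more values are imputed.

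- A simulation of both arms put about 5% of imputed values below -0.5 in each. At 5-30% missing, 5% × 5% = 0.25 and 5% × 30% = 1.5 points, in line with the simulated loss of about 0.2 to 1.6 points per arm. The net effect on the treatment difference was about 0.1 to 0.6 points.
- A less favourable assumption is 80% retention on lebrikizumab, 50% on withdrawal, and 20% imputed in each arm. At SD 1.0 the shares are 12.3% and 2.3%, so the net loss is 20% × (12.3% - 2.3%) = 2.0 points. At SD 0.8 it is 20% × (4.86% - 0.62%) = 0.8 points, and at SD 1.2 it is 20% × (20.5% - 4.8%) = 3.1 points.

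**The case against.** The strongest reply is that nothing in the plan says a value of -1 is a non-responder. The stated reason for rounding is that draws are off the 0-4 grid, so an on-scale result was evidently intended. The Table KGAB.6.11 definition is written for observed scores, not for out-of-range imputations. A sensible programmer would code 1 or less with a reduction of at least 2 and get the right answer. This stands to the extent that non-response follows from a literal reading and is not stated. It does not remove the gap: both codings comply with the text, and for IGA [0] the natural code is equality with 0, which drops the draw.

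A reader might infer a material bias in the primary result. The documents do not support that. At their own planning rates the loss is a fraction of a point and works against lebrikizumab, so it cannot create a false positive on the primary test. Simulating at 46-47% response, above the planning rate, gives 3-4% of imputed values affected, but still only 0.1 to 0.6 points.

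A reader might also infer that at Week 52 the loss falls only on lebrikizumab. It does not. SAP Table KGAB.6.1 restricts the Maintenance Primary Population to patients randomized to lebrikizumab at baseline, so the withdrawal arm also consists of responders to it. A loss within one arm is not a bias in the difference.

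Finally, the NRI and tipping-point analyses do not use these draws. They are free of the problem, but they do not settle how the main analysis is coded.

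**Conclusion.** The gap is real and minor. Rounding without bounding, combined with a response defined by membership of {0, 1}, lets a best-case imputed value count as failure and lets two compliant programs disagree.

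In induction the effect falls almost only on the single lebrikizumab arm. It is about 0.04 to 0.5 points at the planning rates, is conservative, and does not affect the primary conclusion.

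In maintenance it is larger within each arm, about 0.2 to 1.6 points. The net effect on the difference is smaller, about 0.1 to 0.6 points in simulation, although unequal retention and a wider spread could take it to 2 or 3 points.

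The IGA standard deviation, the share of patients imputed, maintenance retention and the simulated correlations are all assumptions. The absence of a bound, and the direction in induction, do not depend on them.

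**What to change.** In SAP 6.4.1.1, with 6.4.2.1 following, state that imputed IGA values are rounded and then truncated to 0-4 before any response is derived. IGA 0/1 then means a truncated value of 1 or less with a reduction of at least 2, and IGA [0] means a truncated value of 0. Either align Protocol 9.4 or record the change in the CSR; SAP 6.1 allows the latter for changes that do not alter a principal feature of the protocol.

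The cost is one sentence and one line of code. Truncating after rounding leaves the imputation model, the draws and the seeds unchanged. It is not quite free in another respect: SAP Version 4 was approved after the study team was unblinded to induction treatment, and the change can only favour lebrikizumab at Week 16. Document it as a correction and report the induction IGA result under both codings. Maintenance assignment was still blinded when that version was approved.

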6.4.1.2. Tipping Point Analysis

Tipping point analysis will be conducted as sensitivity analysis for the primary endpoint of an IGA 0 or 1 and a ≥ 2 -point improvement from Baseline at Week 16 and the following secondary endpoints: EASI-75 and EASI-90 at Week 16 and Pruritus-NRS improvement ≥ 4 -points, at Weeks 1, 2, 4 and 16. For each of these endpoint, the tipping point analysis will only be conducted if its primary or key secondary analyses results are statistically significant.

All subjects who use rescue medication or discontinue treatment due to lack of efficacy will be imputed as nonresponders. Assumptions on missing data as a result of treatment discontinuation due to reasons other than lack of efficacy or any other intermittent missing data will be varied to investigate if there will be any tipping points.

For all the categorical endpoints described above that will be assessed using tipping point analysis, the following process will be used to determine the tipping point:

- Missing responses in the lebrikizumab groups will be imputed with a range of response probabilities, including probabilities of 0, 0.2, 0.4, 0.6, 0.8, and 1.0.
- For missing responses in the placebo group, a range of response probabilities (for example, probability = 0, 0.2 ... 1) will be used to impute the missing values. Multiple imputed dataset will be generated for each response probability.

- Treatment differences between lebrikizumab and placebo are analyzed for each imputed dataset using CMH test (Section 6.1.2). Results across the imputed datasets are aggregated using SAS® Proc MIANALYZE in order to compute a p-value for the treatment comparisons for the given response probability. If the probability values do not allow for any variation between the multiple imputed datasets (for example, all missing responses in the placebo and lebrikizumab groups are imputed as responders and nonresponders, respectively, i.e. extreme case), then the p-value from the single imputed dataset will be used.

For each imputed response probability of Lebrikizumab, the tipping point is identified as the response probability value within the placebo group that leads to a loss of statistical significance when evaluating lebrikizumab relative to placebo.

For tipping point analyses the number of imputed data sets will be $m=25$ and the seed values to start the pseudorandom number generator in SAS are given in [Table KGAB.6.8](#).

Table KGAB.6.8. Seed Values for Tipping Point Analysis

Analysis	Seed value
Proportion of patients achieving IGA of 0 or 1 with a ≥ 2 -point improvement from baseline at Week 16	123470
Proportion of patients achieving EASI-75 and EASI-90 at Week 16	123471
Proportion of patients achieving at least a 4-point improvement from baseline at Weeks 1, 2, 4, and 16	123472, 123473, 123474, 123475 for 4 time points

